## **12.5 Reporting of Pregnancy**

Any pregnancy that starts during the clinical trial must be reported by the investigator to the sponsor and CRO immediately. Pregnancies and pregnancy follow-up should be reported on a Pregnancy Form. Pregnancy follow-up should describe the outcome of the pregnancy, including any voluntary or spontaneous discontinuation; details of the birth; the presence or absence of any congenital abnormalities, birth defects, maternal or newborn complications, and their relation to the IMD. In addition, each pregnancy has to be reported on the AE eCRF page (i.e., as a non-serious AE due to device exposure before or during pregnancy). Pregnancy Forms (including any follow-up forms) should be submitted to the contacts referenced in [Section 12.2.2](#).

If a subject becomes pregnant during the trial, the subject must not receive further treatments (i.e., touch-up treatment); however, the subject will remain in the trial. In cases of pregnancy, clinical laboratory tests will not be performed.

## **12.7 Definition of Device Deficiency**

A device deficiency is defined as an inadequacy of a medical device with respect to its identity, quality, durability, reliability, safety, or effectiveness.

Note: Device deficiencies include malfunctions, use errors, and inadequate labeling.

### **12.7.1 Reporting and Handling of Device Deficiencies**

All device deficiencies shall be documented and reported by the investigator throughout the clinical investigation and appropriately managed by the sponsor.

The investigator should retain the device and/or needle in question for future inspection and investigation by the sponsor, if necessary.

The investigator will attempt to evaluate if the deficiency might have led to an AE if suitable action had not been taken, intervention had not been made, or circumstances had been less fortunate. A device deficiency that could have led to a SADE ([Section 12.4](#)) is to be reported in the same way as an SAE.

For reporting of device deficiencies:

- A Device Deficiency eCRF page must be completed and submitted by the investigator, irrespective of the seriousness of the case.

- A Device Deficiency eCRF page must be completed and submitted by the investigator, irrespective of whether the complaint led to an AE.
- If a device deficiency is associated with an SAE, the investigator must also complete and submit an SAE Report Form (Section 12.2.2) in addition to the Device Deficiency eCRF page.

If a device deficiency is not related to a specific subject (e.g., damaged packaging occurring prior to the subject’s visit), the investigator should complete a paper Device Deficiency Form, instead of the eCRF page, and send immediately to the following contacts:

MERZ	CRO
Global Quality – Complaint Management [REDACTED] Merz Pharma & Co. KGaA Global Quality [name] [REDACTED]	[REDACTED]

The sponsor’s Global Quality department will decide if the device and/or needle needs to be returned and to whom the device and/or needle should be sent for investigation.

## 13 STATISTICAL METHODS

This section describes the statistical analyses foreseen at the time of trial planning. Further details on the statistical and analytical aspects will be presented in the statistical analysis plan (SAP) that will be prepared and completed prior to database close.

Any deviations from planned analyses, the reasons for such deviation, and all alternative or additional statistical analyses that may be performed before database close or unblinding, respectively, will be described in amendments to the CTP and/or the SAP. All deviations and/or alterations will also be summarized in the clinical trial report.

### 13.1 Estimation of Sample Size

The sample size was calculated separately for safety and for the primary effectiveness endpoint as follows:

#### 13.1.1 Safety

The safety aim of the trial is to generate a database with short-term and sufficient long-term safety data. Based on the International Council on Harmonization of Technical Requirements for Registration of Pharmaceuticals for Human Use (ICH) E1 guideline, 100 subjects treated and observed over 48 weeks is deemed sufficient. [REDACTED]

#### 13.1.2 Effectiveness

The sample size considerations for the primary effectiveness endpoint (i.e., change from baseline to Week 24 after last injection on the WSRSS [REDACTED]) are based on the following:

- Type I error,  $\alpha = 0.05$  (two-sided) and
- Non-inferiority margin of 0.5.

When using the 118 subjects randomized for safety and applying a drop-out rate of 15% from randomization to the Per Protocol Set (PPS), [REDACTED], 100 subjects would be available for analysis of the primary effectiveness endpoint on PPS.

For analysis on the Full Analysis Set (FAS) even more subjects are expected. [REDACTED]

To ensure a reasonable number of subjects is enrolled per investigative site, the number of subjects treated at each site should not exceed 20 in case of seven recruiting sites, 24 in case of six recruiting sites, and 28 in case of five recruiting sites.

### 13.2 Randomization

Each subject screened will be given a screening number. Only the subjects who are randomized will receive a randomization number at baseline (V2) through an electronic system. All eligible subjects will be randomized 1:1 to one of the following groups:

- Group 1: left NLF: Radiesse, right NLF: Restylane or
- Group 2: left NLF: Restylane, right NLF: Radiesse.

Randomization will be stratified by investigative site and performed in blocks. All randomization codes will be generated by an electronic system. The system will allocate the subject's randomization number and will determine the subject's group assignment (Group 1 or Group 2) to be used at each injection visit. The randomization number for each subject will then be recorded in the eCRF.

### 13.3 Populations for Analysis

The following analysis sets will be defined:

- The randomized set is defined as all subjects randomized into the trial.
- The Safety Evaluation Set (SES) is defined as all subjects who are randomized and receive investigational product at least once.
- The FAS is defined as all subjects who are randomized, receive investigational product, and have at least one after-baseline effectiveness assessment.
- The PPS is the subset of subjects in the FAS who have no major protocol deviations or other events that impact analysis of the primary effectiveness endpoint. Final determination of which events lead to exclusion from PPS will be made prior to database close.

## 13.4 Analysis of Trial Data

Effectiveness and safety endpoints are provided in [Section 7.2.1](#) and [Section 7.2.2](#) respectively.

All statistical analyses will be performed using Statistical Analysis System (SAS) statistical analysis software [REDACTED].

All safety analyses will use the SES. Effectiveness analyses will be performed on the PPS and for sensitivity on the FAS.

### 13.4.1 Effectiveness Analyses

There will be one confirmatory analysis of the primary effectiveness endpoint. All other analyses are supportive.

#### 13.4.1.1 Primary Effectiveness Endpoint

If the expected mean intra-individual difference between Radiesse and Restylane in WSRS change from baseline to Week 24 is denoted by  $\delta$ , the null and alternative hypotheses to be tested are:

$$H_0 : \delta \geq 0.5 \text{ (null hypothesis ) versus } H_1 : \delta < 0.5 \text{ (alternative hypothesis)}$$

with 0.5 being the non-inferiority margin. To test the null hypothesis, a two-sided 95% CI will be constructed around  $\delta$ .  $H_0$  will be rejected if the upper bound of the two-sided 95% CI lies below the non-inferiority margin of 0.5. It will then be concluded that Radiesse is non-inferior to Restylane and is effective. The two-sided 95% CI for  $\delta$  will be constructed by applying a repeated-measures analysis of covariance (ANCOVA) model to the WSRS change from baseline to Week 24. This model will include treatment (i.e., Radiesse or Restylane), investigative site, touch-up performed (i.e., yes/no), and randomized sequence (i.e., “left NLF treated with Radiesse and right NLF treated with Restylane” or “left NLF treated with Restylane and right NLF treated with Radiesse”) as fixed class effects and baseline WSRS [REDACTED] as a fixed covariate. That observations are dependent over treatment (due to the split-face design) will be modelled using treatment as a repeated factor. The SAS procedure “proc mixed” will be used with the covariance matrix for treatments left “unspecified”. The latter allows estimation of different variances for the two treatments.

The least squares means (lsmeans) statement will be used to derive a point estimate as well as a 95% CI for  $\delta$ .

The confirmatory analysis will be based on the PPS. [REDACTED]  
[REDACTED] he  
variables (VAR) statement will include the variables treatment, investigative site,

randomized sequence, age, sex, touch-up, and WSRS at visits before Week 24. [REDACTED]

[REDACTED]

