### 6.2.1 *Justification of Proposed Trial Design and Primary Effectiveness Endpoint*

This current trial is designed to demonstrate the effectiveness and safety of Radiesse in a split-face trial that compares this CaHA dermal filler to an HA dermal filler, Restylane, for treatment of NLFs. The safety and effectiveness of Radiesse for use as a soft-tissue filler in the NLFs, hands, and face has been demonstrated in other studies, resulting in extensive use worldwide [10-15]. Although Radiesse, as a CaHA, differs from HA fillers in its ultimate mechanism of action, proposed use of a split-face trial design and an active comparator follows China's Center of Medical Device Evaluation (CMDE) guidelines for NLF treatment with dermal fillers. The primary effectiveness endpoint has been chosen to demonstrate that Radiesse will be non-inferior to Restylane for correction of moderate to

severe NLFs when assessed at Week 24. [REDACTED]

[REDACTED] he current proposed trial design and trial duration of 48 weeks are expected to further support the safe and effective use of Radiesse for treatment of NLFs in adults.

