## 8 CLINICAL INVESTIGATION PLAN

### 8.1 Overview of Trial Design

This is a 48-week, prospective, randomized, multicenter, split-face, active-comparator, blinded [REDACTED] trial designed to evaluate the effectiveness and safety of Radiesse compared to Restylane for the correction of moderate to severe NLFs in healthy adult subjects. Those enrolled will have symmetrical NLFs, with the same WSRS score of 3 or 4 (moderate or severe) for both right and left NLFs, as determined on live assessment [REDACTED].

[REDACTED]

All [REDACTED] will be blinded to treatment assignment. [REDACTED] primary effectiveness will be evaluated using the change from baseline to Week 24 after last injection on the WSRS [REDACTED].

Subjects who do not achieve at least 1-point improvement on the WSRS at Week 4 when compared to baseline, [REDACTED] will have a touch-up injection in [REDACTED] NLFs to achieve optimal correction (i.e.,  $\geq 1$ -point improvement). If a touch-up is performed, the same randomized product assigned for the initial injection must be used. [REDACTED]

[REDACTED]

[REDACTED]

[REDACTED]

Standard safety parameters, including documentation of AEs and SAEs, will be assessed. [REDACTED]

After a maximum 10-day screening period, the planned trial duration for individual subjects is 48 weeks ( $\pm 7$  days) after last injection.

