## 8.2 Discussion of Trial Design, Including the Choice of Control Groups

[figure not shown]
As detailed in [Section 8.1](#), this is a 48-week, prospective, randomized, multicenter, split-face, active-comparator, blinded [REDACTED] trial designed to establish that Radiesse is safe and effective for the correction of moderate to severe NLFs by demonstrating non-inferiority to Restylane and by comparing the safety profiles of both products.

Active-controlled clinical studies are considered the standard for clinical investigations whenever proven effective treatments exist on the market for a given condition. A previous study of Radiesse with active HA comparators has demonstrated effectiveness and patient satisfaction for CaHA filler compared to HA in the treatment of NLFs [17]. Restylane will be utilized as the comparator in this proposed trial, as no other CaHA filler is currently marketed in China, and Restylane represents the best possible comparator.

[REDACTED] he trial duration of 48 weeks also represents a reasonable timeframe to assess delayed-onset and/or long-term AEs.

Since subject satisfaction is the primary goal of aesthetic medicine, subjects may undergo a touch-up treatment after initial injection to achieve optimal correction [REDACTED]

[REDACTED] herefore, the choice of active comparator is suitable for demonstration of treatment effectiveness.

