#### 10.1.2 *Comparator Device - Restylane*

Restylane is a clear, transparent, and viscous modified sodium hyaluronate gel for facial-tissue augmentation by injection into the mid-dermis. Restylane contains a gel of modified hyaluronic acid (HA) of nonanimal origin. Hyaluronic acid is a natural macromolecular substance, which occurs as an important structural element in the skin and in subcutaneous and connective tissues, as well as in the synovial tissue and fluid. Hyaluronic acid is metabolized and degraded normally in the body. All raw materials used in the manufacturing process are of nonanimal origin.

Restylane is supplied in a disposable glass syringe at two volumes (0.5 mL/syringe and 1 mL/syringe) with a Luer-lock fitting. The contents of the syringe are sterile. Restylane is packaged with sterilized 29 gauge x 1/2 inch needle to be used for injection into the mid-dermis. The 0.5 mL/syringe package contains one glass syringe with Restylane gel and one needle. The 1 mL/syringe package contains one glass syringe with Restylane gel and two

needles. Restylane will be supplied by the trial sponsor and will be marked for trial-specific clinical use only. Restylane must be used prior to the expiration date printed on the package. It should be stored at a temperature of up to 25° C (77° F). Do not freeze. Protect from sunlight. Do not resterilize Restylane as it may damage or alter the product. Do not use if the package is damaged.

Restylane is intended to be used for facial-tissue augmentation by injection into the mid-dermis to correct moderate to severe NLFs. Restylane should be injected into the middle part of the dermis layer of the facial skin. This product is only intended for use as an intradermal implant, and should not be used for breast injection. Restylane will degrade gradually in the body, typically 6 to 12 months after injection. With degradation, the filler effect will disappear. Patients preferring to maintain the filler effect can receive follow-up injection when the filler effect disappears. [Note: No retreatment injection will be provided under this CTP.] As reported [REDACTED], the filler effect remains for longer than six months in the majority of patients as shown in the Chinese study, where the patients were injected in the NLFs.

[REDACTED]

[REDACTED]

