#### 10.5.1.2 Treatment Administration Procedure

At baseline, all subjects will be randomized and will receive injections in the left NLF with Radiesse and the right NLF with Restylane or vice versa. In this protocol, laterality for injection of trial devices refers to the subject's right or left NLF. The investigator must discuss the potential risks of soft tissue injection with the patient prior to treatment, and make sure that the patient is aware of the signs and symptoms of potential complications. Before the treatment, the patient's suitability for the treatment and the need for pain relief should be assessed. [REDACTED]

Each NLF of each subject will be treated [REDACTED]

[REDACTED] reating investigators will be trained on the WSRS and instructed that when treating subjects, the minimal result to be achieved per NLF is at least 1-point improvement on the WSRS from baseline (i.e., optimal correction).

[REDACTED]

If a touch-up is performed, the same randomized product assigned for the initial injection must be used for touch-up injection. A touch-up treatment will only be administered if there are no medical contraindications or existing AEs of concern, as determined by the treating investigator. [REDACTED]

[figure not shown]
[REDACTED]

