- In addition, the mean treatment difference in WSRS change from baseline to Week 24 after last injection with the associated 2-sided 95% Wald confidence interval will be presented [REDACTED]. The calculation will be performed as follows. First, the treatment difference on the primary endpoint will be calculated for each subject as WSRS change from baseline to Week 24 after last injection at NLF randomized to Radiesse – WSRS change from baseline to Week 24 after last injection at NLF randomized to Restylane. Second, the mean and further metric statistics statistics for continuous endpoints as specified in first paragraph of [Section 6](#) will be calculated for the treatment difference in WSRS change from baseline to Week 24 after last injection. [REDACTED]

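### Does the plan go too far in concluding that Radiesse is effective from non-inferiority to Restylane alone?

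*Protocol*

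**What the plan says.** The confirmatory rule in Protocol 13.4.1.1, repeated in SAP 6.1.1.1, has one condition and two conclusions. If the upper limit of the two-sided 95% CI for δ is below 0.5, "It will then be concluded that Radiesse is non-inferior to Restylane and is effective". SAP 5.1.1 defines change as Week 24 minus baseline, so improvement is negative. SAP 6.1.1 forms the difference as "WSRS change from baseline to Week 24 after last injection at NLF randomized to Radiesse" minus the same quantity on the Restylane side. All other analyses are supportive or exploratory (Protocol 13.4.1 and 13.5.2; SAP 6.4.4).

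The step from non-inferiority to effectiveness is declared in the design sections. Protocol 6.2.1 says that "proposed use of a split-face trial design and an active comparator follows" the Chinese device-evaluation guidelines for fillers in this indication. Protocol 8.2 says the trial is to establish that Radiesse is "safe and effective for the correction of moderate to severe NLFs by demonstrating non-inferiority to Restylane", and after a blacked-out stretch it concludes that "the choice of active comparator is suitable for demonstration of treatment effectiveness".

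Three visible statements bear on the size of the Restylane effect:

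- Protocol 10.5.1.2 instructs investigators that "the minimal result to be achieved per NLF is at least 1-point improvement on the WSRS from baseline".
- Protocol 8.1 provides a touch-up for "Subjects who do not achieve at least 1-point improvement on the WSRS at Week 4 when compared to baseline".
- Protocol 10.1.2 reports for Restylane that "the filler effect remains for longer than six months in the majority of patients as shown in the Chinese study".

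**The concern.** Non-inferiority is a relative statement. If the comparator had little effect at Week 24, a product that did nothing could still lie within 0.5 points of it and be declared effective. No visible part of the criterion requires either fold to have improved. The by-treatment GAIS results are reported but cannot block the conclusion, and no visible figure gives Restylane's expected mean WSRS improvement or ties the 0.5 margin to it.

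Only the words about effectiveness would be at stake. The non-inferiority test, the estimate of δ and the type I error for H0 are untouched.

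**Working it through.** **Inputs from the documents.** Margin 0.5 and α = 0.05 two-sided (Protocol 13.1.2, SAP 3.2); 118 randomized, 15% loss to the PPS, 100 analysed (same sections); paired comparison within subject (Protocol 13.2).

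**Assumed.** The SD of the paired difference, which is not visible: 0.5, 0.7 and 1.0. A paired t-test stands in for the mixed model.

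**The plan's own figures.** 118 × 0.85 = 100.3, so 100 in the PPS is reproduced. The upper limit of a two-sided 95% CI carries a one-sided error of 1 − Φ(1.96) = 0.025. The documents do not print 2.5%; it follows from the two-sided 95% CI.

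**The threshold.** Let r be Restylane's true mean improvement. Then:

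- mean Radiesse change = δ − r;
- rejecting H0 shows δ < 0.5, so mean Radiesse change < 0.5 − r;
- this bound is at or below 0 only if r ≥ 0.5, whatever the SD or sample size.

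**Chance that a Radiesse with zero mean change passes.** Here δ = r, and with n = 100 the probability is P[noncentral t(99 df, (0.5 − r)/(SD/10)) > 1.984]. For r = 0.4 and SD = 0.7 the noncentrality is 0.1/0.07 = 1.43 and the probability is 0.293.

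| Restylane improvement r | SD 0.5 | SD 0.7 | SD 1.0 |
|---|---|---|---|
| 0.30 | 97.7% | 80.8% | 50.8% |
| 0.40 | 50.8% | 29.3% | 16.6% |
| 0.45 | 16.6% | 10.5% | 7.2% |
| 0.50 | 2.5% | 2.5% | 2.5% |
| 0.55 | 0.16% | 0.38% | 0.70% |
| 0.75 | <0.01% | <0.01% | <0.01% |

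With all 118 analysed, r = 0.4 gives 57.7%, 33.7% and 18.9%; r = 0.5 still gives 2.5%.

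**Where r is likely to lie.** Suppose a share p of Restylane folds still shows at least 1 point of improvement at Week 24 and no fold is worse than at baseline (assumption). Then r ≥ p. An r of 0.4 would need at most 40% of folds to keep their point, and an r of 0.3 at most 30%. The protocol points the other way. Each fold is treated to at least 1 point, and subjects short of that at Week 4 get a touch-up. Week 24 is counted from the last injection and is 24 × 7 = 168 days, which is short of six months (about 182 days). Restylane's effect is said to outlast six months in the majority. If that majority keeps at least 1 point, r exceeds 0.5.

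The high percentages also require a Radiesse with no mean improvement at all, although its folds have the same 1-point target and touch-up provision.

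**The case for a change.** The best case for the concern runs as follows. Active-control inference is sound only if the comparator's effect is at least as large as the margin. The rule neither states nor checks that premise. The 1-point target and the touch-up describe correction around treatment, not the Week 24 result, and the statement on duration is qualitative. The trial measures each fold's own change, so a prespecified condition on Radiesse alone would be cheap: with Radiesse truly at zero mean change, adding it held the rate to about 2.6% at most in simulation (SD 0.7 per side, correlation 0.3 or 0.6).

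The threshold of 0.5 stands, and so does the absence of a visible gate. Three things do not follow.

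First, the premise cannot be called missing. The text is blacked out around the design justification (Protocol 6.2.1), the comparator choice (8.2) and the sample size and margin (13.1.2). In 8.2 the conclusion on comparator suitability is legible while its reasons are not. Both reference lists also contain a comparative study of two hyaluronic acid fillers for this indication in a Chinese population (Protocol reference 16, SAP reference 1), which no visible text cites. What the hidden text says is unknown, but it may well be this rationale.

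Second, a condition on Radiesse's own change would add little. It is a before-after comparison with no untreated fold. It would be met with at least 99.8% probability if Radiesse truly improved by 0.5 (SD of its change up to 1.0). It could also be met without any treatment effect. Folds are selected at WSRS 3 or 4, and the screening score serves as baseline (Protocol 9.2.1, SAP 6.4.2). If regression to the mean alone gave 0.2 points (assumed), the condition would be met 98%, 81% or 51% of the time at SD 0.5, 0.7 or 1.0.

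Third, dropping the effectiveness wording would remove the conclusion that Protocol 6.2.1 and 8.2 set as the purpose of the trial. That is a choice of claim, not the repair of a mistake.

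Nor would a failing product stay hidden. Endpoints are assessed separately by product (Protocol 7.2), and the GAIS response rates are reported for each with exact confidence intervals (SAP 6.1.2).

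**Conclusion.** The concern does not hold. It is correct that non-inferiority within 0.5 excludes a zero-improvement Radiesse at 2.5% only when Restylane's true mean improvement is 0.5 or more. That is the ordinary premise of an active-controlled trial, and this plan relies on it openly. The visible text supports the premise, and part of its justification lies under redaction.

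The risk is material only if Restylane retains less than half a point at Week 24 and Radiesse shows no mean improvement: 17% to 51% at r = 0.4, 2.5% at 0.5, below 1% at 0.55 and below 0.01% at 0.75. These figures assume n = 100 and paired SDs of 0.5 to 1.0; the 0.5 threshold itself does not depend on the SD. The view that r below 0.5 is remote assumes that the majority with a lasting effect keep at least 1 point and that folds do not worsen. Wording the conclusion more narrowly would be a matter of preference; the plan contains no error on this point.

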6.1.1 Primary Effectiveness Endpoint

6.1.1.1 Primary analysis

If the expected mean intra-individual difference between Radiesse and Restylane in WSRS change from baseline to Week 24 is denoted by δ , the null and alternative hypotheses to be tested are:

$$H_0: \delta \geq 0.5 \text{ (null hypothesis) versus } H_1: \delta < 0.5 \text{ (alternative hypothesis)}$$

with 0.5 being the non-inferiority margin. To test the null hypothesis, a two-sided 95% CI will be constructed around the estimate for δ . H_0 will be rejected if the upper bound of the two-sided 95% CI lies below the non-inferiority margin of 0.5. It will then be concluded that Radiesse is non-inferior to Restylane and is effective. The two-sided 95% CI for δ will be constructed by applying a repeated-measures analysis of covariance (ANCOVA) model to the WSRS change from baseline to Week 24 after last injection. This model will include treatment (i.e., Radiesse or Restylane), investigative site, touch-up performed (i.e., yes/no), and random group (i.e., "Group 1: left NLF: Radiesse, right NLF: Restylane" or "Group 2: left NLF: Restylane, right NLF: Radiesse")² as fixed class effects and baseline WSRS [REDACTED] as a fixed covariate. That observations are dependent over treatment (due to the split-face design) will be modelled using treatment as a repeated factor. The SAS procedure "proc mixed" will be used with the covariance

² The term "randomized sequence" as used in [Section 13.4.1.1](#) of the protocol was replaced by "random group", as this is the more appropriate term for split-face design studies. Also, the two categories (group 1 and group 2) were relabeled by using the labels from protocol [Sections 10.3](#) and [13.2](#). These changes in terms/ category labels do not constitute any change in planned analyses since the new terms/labels refer to the same variable/ categories.

matrix for treatments left “unstructured”. The latter allows estimation of different variances for the two treatments.

The least squares means (lsmeans) statement will be used to derive a point estimate for δ as well as the associated two-sided 95% CI.

[REDACTED]

[REDACTED]

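### The visible VAR list points to imputation with one record per NLF; if a subject's two sides are then drawn independently, any CI for δ that includes imputed pairs is somewhat too wide

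*Protocol*

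**What the plan says.** Protocol 13.4.1.1 defines δ as the mean within-subject difference between Radiesse and Restylane in WSRS change to Week 24. Non-inferiority is concluded if the upper limit of the two-sided 95% CI is below 0.5. The analysis model respects the pairing. SAP 6.1.1.1 states: "That observations are dependent over treatment (due to the split-face design) will be modelled using treatment as a repeated factor", with an unstructured covariance. SAP 6.1.1 adds a descriptive paired summary: "First, the treatment difference on the primary endpoint will be calculated for each subject".

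After naming the PPS as the set for the confirmatory analysis, and after a redaction, Protocol 13.4.1.1 gives a SAS variable list: "variables (VAR) statement will include the variables treatment, investigative site", then "randomized sequence, age, sex, touch-up, and WSRS at visits before Week 24". More redaction follows. The visible text names neither the procedure, the data layout nor the analysis set to which the list applies. It also does not list the Week 24 score itself.

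Two analysis sets are in play (Protocol 13.4): "Effectiveness analyses will be performed on the PPS and for sensitivity on the FAS". Under Protocol 13.3 the PPS consists of FAS subjects "who have no major protocol deviations or other events that impact analysis of the primary effectiveness endpoint". For the larger set: "The FAS is defined as all subjects who are randomized, receive investigational product, and have at least one after-baseline effectiveness assessment".

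**The concern.** Each subject has Radiesse on one side and Restylane on the other. In a file with one row per subject, `treatment` would have no value to take, and side assignment is already carried by `randomized sequence`. The word therefore has content only with one row per NLF. No variable for the opposite NLF is visible in the list.

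In such a file a standard imputation draws each row's residual independently. A subject who misses Week 24 usually misses it for both sides, so the two imputed scores are linked only through the predictors. The residual side-to-side correlation, which is what makes a split-face comparison precise, is absent from those pairs. The imputation model would then be at odds with the analysis model that follows it. What is at stake is precision and internal consistency, not bias.

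**Working it through.** **The plan's own figure.** 118 randomized and 15% lost before the PPS: 118 × 0.85 = 100.3, and 100 / 0.85 = 117.6, rounded up to 118. The stated 118 and 100 reproduce.

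**Inputs.** From the documents: 118 randomized, 100 in the PPS, margin 0.5, two-sided 95% CI, 5-point ordinal WSRS (Protocol 11.2.1.1). Assumed, because no value is visible: residual side-to-side correlation ρ of 0.3 to 0.7; 6, 12 or 18 of 118 subjects imputed (5, 10, 15%), both NLFs missing together; SD 0.7 per NLF; two earlier visits, all visit correlations 0.5. The 18 is 118 − 100. It is an upper bound, reached only if everyone lost before the PPS stays in the FAS without a Week 24 score.

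**Closed form.** Let V be the variance of the within-subject difference, f the share of subjects imputed, and R² the share of V explained by the predictors. Assume the same ρ before and after conditioning on the predictors, and many imputations.

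- Joint draw: total variance = (V/n)·[1 + (1 − R²)·f/(1 − f)].
- Independent draws: the residual variance of an imputed difference is V(1 − R²)/(1 − ρ) instead of V(1 − R²), an excess of V(1 − R²)·ρ/(1 − ρ). It enters the within-imputation variance with weight f and the between-imputation variance with weight f + f²/(1 − f).
- Hence (SE ratio)² = 1 + (1 − R²)·[2f + f²/(1 − f)]·[ρ/(1 − ρ)] / [1 + (1 − R²)·f/(1 − f)].

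Two earlier visits with correlation 0.5 give R² = 2 × 0.5² / (1 + 0.5) = 1/3. For f = 18/118 = 0.1525, the numerator factor is (2/3) × (0.3051 + 0.0275) = 0.2217 and the denominator is 1 + (2/3) × 0.18 = 1.12, so their quotient is 0.198. At ρ = 0.5: √(1 + 0.198 × 1) = 1.095. At ρ = 0.7: √(1 + 0.198 × 2.333) = 1.209.

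**Simulation.** Bayesian regression imputation, 20 imputations, Rubin's rules, paired-difference analysis, 400 trials per scenario. SE of δ with NLF rows divided by SE with subject rows, n = 118:

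| Imputed | Method | ρ = 0.3 | ρ = 0.5 | ρ = 0.7 |
|---|---|---|---|---|
| 6 | closed form | 1.014 | 1.033 | 1.076 |
| 6 | simulated, continuous | 1.014 | 1.032 | 1.074 |
| 6 | simulated, 5-point | 1.009 | 1.022 | 1.046 |
| 12 | closed form | 1.028 | 1.065 | 1.145 |
| 12 | simulated, continuous | 1.022 | 1.059 | 1.139 |
| 12 | simulated, 5-point | 1.013 | 1.042 | 1.089 |
| 18 | closed form | 1.042 | 1.095 | 1.209 |
| 18 | simulated, continuous | 1.035 | 1.088 | 1.209 |
| 18 | simulated, 5-point | 1.022 | 1.062 | 1.126 |

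A repeat simulation over the same ranges gave 1.01 to 1.20 for continuous and 1.01 to 1.14 for ordinal scores.

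**Limits of the effect.**

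- With f = 0 the ratio is exactly 1. With 5 imputed of 100 (a possible PPS case) it is 1.010 to 1.073 continuous and 1.010 to 1.044 ordinal.
- At ρ = 0 there is no widening (simulated 0.987 to 1.000). At ρ = −0.2 the interval is slightly narrower (0.975 to 0.998).
- Weaker predictors enlarge the effect. At 15% imputed and ρ = 0.7, one earlier visit with correlation 0.5 (R² = 0.25) gives 1.227, and R² = 0 gives 1.284.
- Adding the opposite side's earlier scores as predictors does not help: 1.07 at ρ = 0.5 with 10% imputed, 1.24 at ρ = 0.7 with 15% imputed (one earlier visit).

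**On the WSRS scale.** In the most affected case (18 imputed, ρ = 0.7) the CI half-width is 0.128 against 0.105 for continuous scores and 0.147 against 0.131 for ordinal ones, so the upper limit moves by about 0.02. The largest half-width in any scenario with ρ from 0.3 to 0.7 is 0.18. The empirical SD of the estimate agrees between layouts to within 0.002.

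**Against complete cases.** A separate run of 18 imputed and ρ = 0.7, continuous scores, gave half-widths of 0.129 (NLF rows), 0.108 (complete cases) and 0.106 (joint). NLF rows were wider than complete cases at every positive correlation tried.

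**The case against.** The strongest objection is that the sentence is a fragment between redactions. Protocol section 13 defers detail to the SAP. The SAP defines VAR in its abbreviations but never uses it in visible text, so the governing specification is probably blacked out and may already impute both sides jointly. The visible list does not even contain the score to be imputed, so it cannot be the whole specification. All of this stands. It makes the point conditional and turns it into a request to confirm. It does not explain `treatment` in the list, which has no role in a joint layout.

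It is also right that layout alone does not widen the interval. Three further conditions are needed: independent draws for the two sides, positive residual correlation, and at least some imputed pairs. The visible text states none of them.

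Four stronger readings are tempting, and the documents do not support them:

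- That the problem sits mainly in the FAS sensitivity analysis. The FAS definition makes more missing Week 24 scores plausible there, but the list follows the sentence on the PPS and its scope is not visible.
- That the confirmatory result is invalid or type I error inflated. An interval that is too wide is conservative for non-inferiority.
- That the full 15% loss to the PPS means missing Week 24 scores. It may include subjects with protocol deviations whose scores were recorded.
- That the plan leaves PPS membership open. Protocol 13.3 defers that determination to before database close, so nothing is asked for here.

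**Conclusion.** The point holds in conditional form and at low severity. The visible list implies one record per NLF. If each subject's two sides are then drawn independently and the residual side-to-side correlation is positive, the CI for δ in any analysis with imputed pairs is somewhat too wide. With ρ of 0.3 to 0.7, 5 to 15% imputed and two earlier visits correlated at 0.5, the excess is roughly 1 to 14% for ordinal scores and up to about 21% for continuous ones. The ordinal figures are the more relevant for the WSRS. All of these inputs are assumptions. The estimate of δ is essentially unchanged, and half-widths of at most 0.18 leave the non-inferiority conclusion safe unless δ is near 0.5. A reader might infer a demonstrated error in the plan; the redactions do not allow that. What remains is a cheap gain in precision, since under this reading imputation would do worse than leaving the subjects out.

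**What to change.** Unless the redacted text already does so, impute with one row per subject. Put the Radiesse-side and Restylane-side WSRS at baseline, at earlier visits and at Week 24 together in the VAR list, and drop `treatment`. The other listed variables stay. Then reshape each completed data set to one row per NLF for PROC MIXED, which is unchanged. If joint imputation is already specified, only the word `treatment` needs to be reconciled with it.

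The cost is a transpose before and after imputation and an edited variable list. No new data are needed, and the estimand, margin and analysis model stay as they are.
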